**Regeneron Pharmaceuticals, Inc.** 

- To assess additional subclasses of serum antibodies (eg, total IgG and IgG4 against birch pollen and Bet v 1) to evaluate the relationship between endogenous anti-Bet v 1 antibodies and response to REGN5713-5714-5715
- To assess the reduction in PFAS and related symptoms as measured by pollen food allergy symptom questionnaire (PFASQ)
- To assess patient rating of severity of seasonal allergy symptoms as measured by patient global impression of severity (PGI-S)

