#### 11.4.3. Efficacy Analyses

#### 11.4.3.1. Primary Efficacy Analysis

The efficacy endpoints will be analyzed using the FAS defined in Section 11.3.1.

The primary analysis will focus on the comparison between the REGN5713-5714-5715 arm and placebo arm. The average CSMS during birch pollen season will be compared in subjects receiving REGN5713-5714-5715 and subjects receiving placebo using a linear mixed-effect model, with the treatment group and randomization stratification factors (as described in Section 8.5) as fixed effects and pollen region as a random effect, to account for potential differences in birch pollen seasons based on the geographical location of each pollen region. Clinical sites will be pooled into different pollen regions which will be specified in the SAP. Subjects with at least 1 day of post-baseline diary record with symptom and medical score (SMS) will be included. The CSMS will be calculated on all available data during the birch pollen season. The primary analysis will be based on the available values of daily symptom score and daily medication score to calculate the average CSMS and no imputation will be needed for the primary endpoint during the birch pollen season.

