## **11.4.3.3.** Exploratory Efficacy Analysis

Exploratory efficacy endpoints, including the average ACQ-5, RQLQ (S), and PGI-S scores during the birch pollen season will be analyzed in the same fashion as the primary analysis for the subjects receiving REGN5713-5714-5715 versus placebo. Subjects with at least 1 day of data will be included in the analysis.

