1.2.3. Modifications from the Statistical Section in the Final Protocol

• The per protocol analysis set (PPS) was removed since estimands are constructed with aligned method of analysis that better address the objective, and analysis of PPS might not provide additional insights.

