4.5.3. Exploratory Efficacy Variables

Exploratory efficacy endpoints include:

- RQLQ (S), averaged over the duration of the birch pollen season, for REGN5713-5714- 5715 versus placebo
- ACQ-5, averaged over the duration of the birch pollen season, for REGN5713-5714-5715 versus placebo (only for patients with asthma)
- Change and percent change from baseline to the end of study in SPT mean wheal diameter for birch homologous/cross-reactive allergens in REGN5713-5714-5715 versus placebo
- Baseline allergen-specific IgE levels and correlation with average CSMS, TSS, TNSS, TOSS, DMS during birch pollen season
- Number of baseline sensitizations to other allergens (poly/mono-sensitization status, based on allergen-specific IgE levels) and correlation with CSMS, TSS, TNSS, TOSS, and DMS, averaged over the duration of the birch pollen season
- Baseline serum antibody levels and correlation with CSMS, TSS, TNSS, TOSS, and DMS, averaged over the duration of the birch pollen season

Regeneron Pharmaceuticals, Inc. Statistical Analysis Plan

- To assess the reduction in PFAS and related symptoms, as measured by PFASQ, from baseline to end of study
- To assess patient rating of severity of seasonal allergy symptoms, as measured by PGI-S, from baseline to end of study

Standardized Rhinoconjunctivitis Quality of Life Questionnaire [RQLQ (S)]

The RQLQ (S) has 28 questions in 7 domains: activity limitation, sleep problems, nose symptoms, eye symptoms, non-nose/eye symptoms, practical problems, and emotional function. There are 3 subject-specific questions in the activity domain that allow subjects to select 3 activities in which they are most limited by their rhinoconjunctivitis. Subjects recall how bothered they have been by their rhinoconjunctivitis during the previous week and respond to each question on a 7-point scale (0 [not impaired at all] to 6 [severely impaired]). The overall RQLQ (S) score is the mean of all 28 responses, and the individual domain scores are the means of the items in those domains (Juniper, 1991). The RQLQ (S) will be recorded using an e-diary.

Asthma Control Questionnaire

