The ACQ measures the adequacy of asthma control and change in asthma control that occurs spontaneously or as a result of treatment. The ACQ-5 is comprised of 5, patient-reported items that were rated by clinicians as the most important to evaluate control: (1) awakening at night due to symptoms, (2) morning symptoms, (3) limitation of daily activities, (4) shortness of breath, and (5) wheezing. The total score ranges from 0 to 6 with higher scores denoting less asthma control. A score of ≥ 1.5 is considered as uncontrolled asthma. The ACQ-5 will be recorded using an e-diary for patients with asthma.

Pollen Food Allergy Symptom Questionnaire (PFASQ)

The PFASQ will be performed to determine the types of food that produce an allergic reaction, the type of reaction, and how soon the reactions occur.

Patient Global Impression of Severity (PGI-S)

The PGI-S assesses the severity of seasonal allergy symptoms over the past 1 week. Symptom severity ranges from 0 (no symptoms), 1 (mild), 2 (moderate), and 3 (severe) symptoms.

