5.6.5. Analysis of Exploratory Efficacy Variables

For continuous exploratory efficacy variables, e.g. average ACQ-5 and change and percent change in SPT mean wheal diameter for birch homologous/cross-reactive allergens, they will be analyzed by using a linear mixed effects model similar to the analyses of primary endpoint.

For categorical exploratory variables, e.g. PFASQ and PGI-S, only descriptive summary will be provided.

For endpoints related to biomarker, e.g. serum total IgE, serum sIgE for birch and Bet v 1, analysis method will be detailed in section 5.11.

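### SAP 5.6.5 gives the ordered 0–3 PGI-S a descriptive summary only, where Protocol 11.4.3.3 plans a between-arm comparison, and SAP 1.2.3 does not declare the change

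*SAP*

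**What the plan says.** **Protocol.** Section 11.4.3.3 covers PGI-S together with the asthma and quality-of-life scores: "Exploratory efficacy endpoints, including the average ACQ-5, RQLQ (S), and PGI-S scores during the birch pollen season will be analyzed in the same fashion". The method meant is that of the primary analysis, and the contrast is active treatment versus placebo. Section 11.4.3.1 defines that analysis as a comparison "using a linear mixed-effect model, with the treatment group and randomization stratification factors (as described in Section 8.5) as fixed effects", with pollen region as a random effect.

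**SAP.** Section 4.5.3 describes an ordered scale: "Symptom severity ranges from 0 (no symptoms), 1 (mild), 2 (moderate), and 3 (severe) symptoms". It gives the endpoint as "To assess patient rating of severity of seasonal allergy symptoms, as measured by PGI-S, from baseline to end of study". Section 5.6.5 then splits the exploratory variables into two groups. Of the continuous ones, with ACQ-5 among the examples, it says "they will be analyzed by using a linear mixed effects model similar to the analyses of primary endpoint". Of the others it says "For categorical exploratory variables, e.g. PFASQ and PGI-S, only descriptive summary will be provided".

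**Declared changes.** SAP 1.2.3 is the section for departures from the protocol's statistical section. It has one entry: "The per protocol analysis set (PPS) was removed since estimands are constructed with aligned method of analysis". PGI-S is not mentioned there, nor in the amendment history in SAP 1.2.4, which concerns prohibited medications.

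**The concern.** Protocol 3.2.1 explains that PGI-S is given to learn how treatment affects the patient's overall impression of severity. That is a question about a difference between randomized arms. A table of category percentages by arm lets a reader see a difference but attaches no estimate or interval to it, and makes no use of the stratification factors.

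The change is also hard to find. Someone who checks SAP 1.2.3 to learn what differs from the protocol would conclude that the modelled PGI-S comparison still stands. At stake are the interpretability of one exploratory endpoint, which is the trial's only patient global rating of seasonal severity, and the traceability of the SAP to the protocol.

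**Working it through.** No figure in the documents bears on PGI-S, so the check compares the texts.

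1. **Is the protocol commitment a between-arm model?** Yes. Section 11.4.3.3 names PGI-S and refers to the primary method, which 11.4.3.1 defines as a linear mixed-effect model with treatment as a fixed effect. Its product is a treatment difference.

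2. **What does a descriptive summary contain?** SAP section 5 specifies frequencies and percentages per category for categorical or ordinal data. So all four levels are displayed, in order, without a contrast.

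3. **Does another SAP section restore a contrast?**
   - 5.6.3 (hierarchy): the primary endpoint and six secondary tests; no PGI-S.
   - 5.6.4 (subgroups): primary endpoint only.
   - 5.11 (biomarkers): correlations with primary and secondary endpoints only.
   - Table 10.1.1: stops at the secondary endpoints.
   - 6.4 (visit windows): assigns PGI-S to baseline, Visit 5 (days 2 to 85) and Visit 7 (day 86 onward), but names no analysis.

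   None does.

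4. **Is the change declared?** Not in SAP 1.2.3 or 1.2.4.

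5. **Could the protocol sentence simply be reinstated?** Not as it stands. It speaks of an average over the birch season, whereas Protocol 4.3 and SAP 4.5.3 define the endpoint from baseline to end of study. The nominal schedule shows the difficulty:
   - Randomization (day 1) falls about 2 weeks before the season.
   - Visit 5 (day 57) is planned within 2 weeks of the anticipated local peak.
   - The telephone contact that Protocol 3.2.1 places at the end of the season is Visit 6 (day 85).
   - Visit 7 is day 113, and 113 − 85 = 28 days later. The PGI-S looks back one week.

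   Nominally, then, only Visit 5 yields an in-season PGI-S, and a seasonal average reduces to that one value. The ±14-day windows can close the gap for an individual (85 + 14 = 99 and 113 − 14 = 99), and timing varies by site, so this describes the usual case. Any restored comparison has to name its visits.

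**The case against.** The strongest reply is that the SAP is within its remit. PGI-S is exploratory. Protocol section 11 presents itself as the basis for the SAP and allows later changes. Tabulating a four-level exploratory item is a respectable choice, and SAP 5.6.5 states it openly. The protocol's version was also barely workable, as the schedule shows.

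Most of this stands. It rules out several stronger readings that a reader might infer:

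- **That confirmatory conclusions are at risk.** They are not. PGI-S is absent from the hierarchy in SAP 5.6.3.
- **That PGI-S yields no information, or that its ordering is thrown away.** All four ordered percentages will be shown by arm. Only the contrast and its uncertainty are missing.
- **That a stated amount of power is lost.** The documents give no PGI-S distribution, standard deviation or target effect. Any power figure would rest on invented distributions. A comparison with the share scoring 2 or more would be against an analysis that the SAP does not plan.
- **That the SAP may not depart from the protocol, or conceals that it does.** It may depart, and the choice is written in 5.6.5. The fault is that it is neither listed nor explained in 1.2.3.
- **That the same departure affects PFASQ.** Protocol 11.4.3.3 does not name PFASQ, so the mismatch is established for PGI-S only.

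The reply does not account for the missing declaration. A poorly specified protocol analysis is a reason to specify it better, or to record its removal.

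**Conclusion.** The point holds as a minor one. For PGI-S, SAP 5.6.5 replaces a planned model-based comparison with category frequencies and percentages. No other section supplies a between-arm estimate or interval, and the departure is not declared. It concerns one exploratory endpoint, with no effect on type I error or on any confirmatory result. Its size cannot be given as a number from these documents.

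The conclusion rests on two readings: that a descriptive summary means what SAP section 5 says for ordinal data, and that SAP 1.2.3 is meant to be a complete list of departures. The contrast with the other scores in the same protocol sentence is explicit for ACQ-5. For RQLQ (S), which SAP 5.6.5 does not name, it is an inference from that score being a mean of 28 items and so falling under the rule for continuous variables.

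**What to change.** In SAP 5.6.5, take PGI-S out of the descriptive-only sentence and add an analysis along these lines:

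- **Scale and visits:** compare arms on the full 0–3 score at Visit 5, for the protocol's in-season comparison, and at Visit 7, for the baseline-to-end-of-study endpoint, using the existing SAP 6.4 windows.
- **Model:** choose one before database lock. Either a proportional-odds model or the protocol's linear mixed model would serve, with treatment, the randomization stratification factors and baseline PGI-S. The baseline score is an addition to the primary model's terms and matches the stated endpoint.
- **Reporting:** between-arm estimate, 95% CI and a nominal p-value, labelled as outside the hierarchy. Keep the category table beside it.

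If the sponsor does intend a descriptive summary only, list that in SAP 1.2.3 as a change from Protocol 11.4.3.3 and give the reason.

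The first route needs a short SAP edit and one model at each of two visits, on data already scheduled and windowed. Its downside is one or two more nominal, unadjusted exploratory p-values. The second route costs one line and a justification, and leaves the treatment contrast unestimated.

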5.7. Analysis of Safety Data

The analysis of safety and tolerance will be performed on the SAF, as defined in Section 3.2.

The safety analysis will be based on the reported AEs, clinical laboratory evaluations and vital signs.

Thresholds for treatment-emergent Potential Clinically Significant Values (PCSV) in laboratory variables and vital signs are defined in Appendix 10.3. Treatment-emergent PCSV is any PCSV developed or worsened in severity compared to the baseline during the treatment and follow-up period. The baseline when determining treatment-emergent PCSV refers to the baseline value of the study.

The time interval to detect any event or abnormality is between the first injection of study medication and EOS.

5.7.1. Adverse Events

The number and proportion of subjects reporting TEAEs will be summarized on SAF as described in Section 3.2.

AE incidence tables will be presented by treatment group for the SAF as well as subgroups for safety. TEAE summaries will present the number (n) and percentage (%) of subjects experiencing an TEAE by SOC and PT, sorted by decreasing frequency of SOC and PT for the REGN 5713-5714-5715 treatment group. Multiple occurrences of AEs of the same PT (or SOC) in the same subject will be counted only once for that PT (or SOC). For tables presenting severity of events, the worst severity will be chosen for subjects with multiple instances of the same event. The denominator for computation of percentage is the number of subjects in each treatment group for safety analysis.

An overall summary of TEAEs will be provided with number and proportion of subjects with any:

- TEAE
- Serious TEAE

Regeneron Pharmaceuticals, Inc. Statistical Analysis Plan

- Serious TEAE leading to death
- Study drug related TEAE/serious TEAE
- TEAE leading to study discontinuation
- Maximum intensity for TEAE

Note: TEAE leading to treatment discontinuation will be not provided since the study only has a single dose.

Detailed summaries of TEAEs will include:

- TEAEs
 - TEAEs by primary SOC/PT
 - TEAEs by PT
 - TEAEs by primary SOC/PT with incidence of $PT \ge 5\%$
 - TEAEs by severity and by primary SOC/PT
 - TEAEs related to study drug as assessed by the investigator by primary SOC/PT
- Serious TEAE
 - Serious TEAEs by primary SOC/PT
- Fatal AEs by primary SOC/PT
- TEAE leading to study discontinuation by primary SOC/PT
- AESI by AESI category (see section 10.4), primary SOC/HLT/PT

Number and proportion of subjects reporting pre-treatment adverse events will be tabulated by primary SOC and PT.

The number and proportion of subjects with injection site reaction by PT will be summarized.

5.7.2. Clinical Laboratory Measurements

Laboratory measurements include clinical chemistry, hematology and urinalysis results, and will be converted to standard international units. Summaries of laboratory variables will include:

- Descriptive statistics of laboratory result and change from baseline by visit
- The number (n) and percentage (%) of subjects with treatment-emergent PCSVs. This summary will be provided based on the subgroup of SAF subjects who did not meet the PCSV criterion at baseline
- Shift tables based on baseline normal/abnormal and other tabular and graphical methods may be used to present the results for parameters of interest

The graph of mean change and/or percent change from baseline value for lab parameters by visit will be provided.

5.7.3. Analysis of Vital Signs

Summaries of vital sign variables will include:

- Descriptive statistics of vital sign variable and change from baseline by visit
- The number (n) and percentage (%) of subjects with treatment-emergent PCSV
- Shift tables based on baseline normal/abnormal and other tabular and graphical methods may be used to present the results for parameters of interest

5.8. Analysis of Pharmacokinetic Data

Descriptive statistics of total REGN51713, total REGN5714, total REGN5715, and total drug (REGN5713+REGN5714+REGN5715) concentrations in serum at each sampling timepoint will be provided. Plots of mean concentration versus nominal time will be presented. Select PK parameters may be calculated.

Exposure-response analysis for biomarkers, efficacy, and safety endpoints may be conducted as appropriate, and presented in separate reports.

5.9. Analysis of Immunogenicity Data

5.9.1. Analysis of ADA Data

The immunogenicity variables described in Section 4.8 will be summarized using descriptive statistics. Analysis described in this section will be performed separately for ADA to REGN5713, ADA to REGN5714 and ADA to REGN5715 in all treatment groups unless otherwise specified.

The following analysis will be provided by treatment groups and ADA titer categories:

- Number (n) and percent (%) of ADA-negative subjects
- Number (n) and percent (%) of pre-existing immunoreactivity subjects
- Number (n) and percent (%) of treatment-emergent ADA positive subjects
- Number (n) and percent (%) of treatment-boosted ADA positive subjects

5.9.2. Analysis of Neutralizing Antibody (NAb) Data

Anti-REGN5713, REGN5714, and REGN5715 neutralizing antibodies (NAb) analysis may be performed on ADA-positive serum samples. The overall immunogenicity risk will be taken into consideration to assess the need for NAb analysis. Serum samples will be banked, if NAb analysis is to be conducted at a later time.

The absolute occurrence (n) and percent of subjects (%) with NAb status in the NAb analysis set will be provided by treatment groups. Analysis described in this section will be performed separately for NAb to REGN5713, NAb to REGN5714 and NAb to REGN5715 in all treatment groups unless otherwise specified.

5.10. Association of Immunogenicity with Exposure, Safety and Efficacy

5.10.1. Immunogenicity and Exposure

Potential association between immunogenicity variables and systemic exposure to REGN5713, REGN5714 or REGN5715 will be explored. Plots of drug concentration may be provided for analyzing the potential impact of ADA response status, titer and NAb status on PK.

5.10.2. Immunogenicity and Safety and Efficacy

Potential association between immunogenicity variables and safety may be explored with a primary focus on the following safety events during the TEAE period:

- TEAEs
- SAEs
- Injection site reaction (HLT: Injection site reaction)
- Hypersensitivity (SMQ: Hypersensitivity [Narrow] followed by manual adjudication (same as AESI 'Hypersensitivity'))
- Anaphylaxis (SMQ: Anaphylactic Reaction [Narrow])

Note: TEAE leading to treatment discontinuation will be not provided since the study only has a single dose.

Potential association between immunogenicity variables and efficacy endpoints may be explored in the study (e.g. scatter plot or spaghetti plot).

The safety and efficacy analyses mentioned above will be conducted using the following categories:

- ADA positive subjects, that is subjects/patients with treatment-emergent or treatment-boosted response.
- ADA negative subjects, that is subjects/patients with pre-existing immunoreactivity or negative in the ADA assay at all time points.
- NAb positive subjects, that is ADA positive subjects who were positive in the NAb assay at any time point analyzed.
- Maximum post-baseline titer in treatment-emergent or treatment-boosted ADA positive subjects:
 - Low (titer <1,000)
 - Moderate $(1,000 \le \text{titer} \le 10,000)$
 - High (titer >10,000)

5.11. Analysis of Biomarker Data

All biomarker analyses will be performed on the FAS using all observed data.

Descriptive statistics for the observed values and change and percent change from baseline in detectable allergen specific IgE by treatment and visit will be provided for the biomarker variables.

Baseline serum total IgE, serum birch pollen sIgE, and serum bet v 1 sIgE and the ratio of serum Bet v 1 sIgE/ serum birch pollen sIgE will be correlated to the primary and secondary clinical efficacy endpoints using spearman's rho test.

The percent of detectable IgE at each visit (V5 and V7) compared to baseline will also be correlated to the primary and secondary clinical efficacy endpoints using spearman's rho test. Both the spearman correlation coefficients and p-values will be reported. Multiple linear regression models will also be used to explore these relationships, with the efficacy endpoints as dependent variables and the IgE values at baseline (log transformed if appropriate) as dependent variables.

The poly-allergen sensitization status for each study subject will be determined by the number of allergen-specific IgE values that are equal to or above 0.35kUa/L. A descriptive report will be provided based on the allergen-specific IgE results at screening/ baseline for all concomitant or homologous allergen to birch pollen. The number of allergen that each subject were sensitized to will be correlated with the primary and secondary clinical outcomes.

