# 2.3. Exploratory Objectives

The exploratory objectives are:

- To assess asthma control as measured by the asthma control questionnaire (ACQ-5)
- To assess quality of life as measured by the rhinoconjunctivitis quality of life questionnaire (RQLQ [S])
- To evaluate the reduction in early allergic response to birch homologous allergens (alder and oak) as measured by SPT mean wheal diameter
- To assess the relationship between allergy sensitization status to Bet v 1 or birch pollen at screening (as measured by serum allergen specific-IgE [sIgE]) and clinical response to REGN5713-5714-5715 treatment
- To assess serum sIgE levels against Bet v 1 and birch pollen during birch pollen season to evaluate the relationship between the response to REGN5713-5714-5715 and change in sIgE levels in-season
- To assess the inhibitory effect of REGN5713-5714-5715 on the binding of endogenous serum IgE to birch allergen in an in vitro assay; to assess whether the degree of inhibition correlates with clinical improvement
- To assess sIgE levels against other allergens (eg, Bet v 2, alder and oak) at screening and to evaluate the relationship between response to REGN5713-5714-5715 and polyallergic status

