# 4.3. Exploratory Endpoints

The exploratory endpoints are:

- ACQ-5, averaged over the duration of the birch pollen season, for REGN5713-5714-5715 versus placebo
- RQLQ (S), averaged over the duration of the birch pollen season, for REGN5713-5714-5715 versus placebo
- Change and percent change from baseline to the end of study in SPT mean wheal diameter for birch homologous/cross-reactive allergens in REGN5713-5714-5715 versus placebo
- Baseline allergen-specific IgE levels and correlation with average CSMS, TSS, TNSS, TOSS, DMS during birch pollen season
- Change and percent change from baseline to the peak of birch pollen season in allergenspecific IgE
- Change in inhibitory effect on serum IgE to birch allergen
- Number of baseline sensitizations to other allergens (poly/mono-sensitization status, based on allergen-specific IgE levels) and correlation with CSMS, TSS, TNSS, TOSS, and DMS, averaged over the duration of the birch pollen season
- Baseline serum antibody levels and correlation with CSMS, TSS, TNSS, TOSS, and DMS, averaged over the duration of the birch pollen season
- To assess the reduction in PFAS and related symptoms, as measured by PFASQ, from baseline to end of study
- To assess patient rating of severity of seasonal allergy symptoms, as measured by PGI-S, from baseline to end of study

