#### 9.2.7.2. Serum Antibodies

Levels of anti-birch pollen sIgE and anti-Bet v 1 sIgE will be measured according to Table 1 to evaluate the relationship between clinical response to REGN5713-5714-5715 and sensitization to birch pollen and Bet v 1. After the randomization visit, the detection of anti-Bet v 1 sIgE will be inhibited by study drug REGN5713-5714-5715, therefore the data will be used to assess effective competition between endogenous sIgE and study drug.

Serum total IgE will be measured according to Table 1 to assess the overall allergic disease burden in study subjects. The results will be used to evaluate the relationship between response to REGN5713-5714-5715 and overall allergic status.

Allergen-specific IgE levels against regional allergens and common perennial allergens will be measured according to Table 1 to assess sensitization status to other common allergens and to evaluate the relationship between response to REGN5713-5714-5715 and poly/mono-sensitization (Van Ree, 1999).

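### The post-dose IgE correlations in SAP 5.11 are not split or adjusted by arm although the drug masks Bet v 1 IgE, and the baseline IgE regression has no treatment term

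*SAP*

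**What the plan says.** SAP 5.11 sets the population: "All biomarker analyses will be performed on the FAS using all observed data". Arm is mentioned only for the descriptive summaries: "change and percent change from baseline in detectable allergen specific IgE by treatment and visit will be provided".

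Four association analyses against the primary and secondary efficacy endpoints follow, none with an arm split or a treatment term:

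- Spearman correlations of baseline IgE measures.
- A post-dose correlation: "The percent of detectable IgE at each visit (V5 and V7) compared to baseline will also be correlated". The sentence does not name the allergen.
- Multiple linear regression of the efficacy endpoints, with "the IgE values at baseline (log transformed if appropriate) as dependent variables". The outcomes are given the same label, so the predictors are mislabelled.
- A correlation with the number of sensitizations.

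For the Spearman analyses, "Both the spearman correlation coefficients and p-values will be reported".

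Protocol 9.2.7.2 says that after randomization "the detection of anti-Bet v 1 sIgE will be inhibited by study drug REGN5713-5714-5715", and that the later data serve to assess competition between drug and endogenous sIgE. Protocol 2.3 asks about response to treatment: "To assess the relationship between allergy sensitization status to Bet v 1 or birch pollen at screening" and clinical response to the drug, and separately the link between response and in-season sIgE change. Protocol 4.3 lists as an endpoint "Change and percent change from baseline to the peak of birch pollen season" in allergen-specific IgE.

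**The concern.** There are two separate problems.

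**Post-dose IgE (V5, V7).** If the drug suppresses detectable Bet v 1 sIgE, low values cluster in the active arm. If the drug also lowers CSMS, low scores cluster there too. Pooling the arms then produces a positive correlation even if, within each arm, a subject's detectable IgE says nothing about that subject's symptoms. A small p-value could be read as showing that subjects with more IgE blocked do better, when it mostly repeats the randomized comparison in SAP 5.6.1.

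**Baseline IgE.** This is measured before dosing, so masking cannot touch it. But a model with baseline IgE alone shows whether sensitized subjects have worse seasons (prognosis). It cannot show whether the drug's benefit varies with sensitization, which is what Protocol 2.3 asks.

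**Working it through.** **Inputs.** From SAP 2.3: 120 per arm after 20% dropout from 150, CSMS means 6.3 and 4.4, SD 4.5, two-sided alpha 0.05. From Protocol 11.2: smallest significant difference 1.14. The size of masking is in neither document. I take it as a downward shift of 0.5 to 8 within-arm SD in the active arm.

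**The plan's own figures reproduce.**

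- Power: 1.9/4.5 = 0.422; 0.422/√(2/120) = 3.27; Φ(3.27 − 1.96) = 0.905 (0.903 by the t distribution), against the stated 90%.
- Sample size: 120/(1 − 0.2) = 150.
- Smallest significant difference: 1.96 × 4.5 × √(2/120) = 1.14.

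**Expected pooled correlation under complete separation.** The correlation of arm with CSMS is 0.422/√(0.422² + 4) = 0.207. When the arms do not overlap on IgE, the rank of IgE correlates with arm at √(12/16) = 0.866. The product is 0.207 × 0.866 = 0.18, with no within-arm link at all. Simulation gives a mean rho of 0.176 with normal CSMS and 0.242 with gamma CSMS.

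**How often pooled Spearman gives p<0.05** (simulated, 120 per arm, no within-arm link):

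| Masking (within-arm SD) | Difference 1.9, normal | Difference 1.9, gamma | Difference 1.14, normal | No effect, normal |
|---|---|---|---|---|
| 0.5 | 12% | 18% | 7% | 5% |
| 1 | 28% | 52% | 15% | 5% |
| 2 | 64% | 88% | 29% | 5% |
| 8 | 78% | 97% | 37% | 6% |

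At 1.14 with gamma CSMS the rates are 20%, 45% and 59% for 1, 2 and 8 SD. With 150 per arm, normal CSMS, difference 1.9 and 8 SD, the rate is 87%. Repeat runs differ by a point or two, so I quote the ranges for 120 per arm as 11–79% (normal, 1.9), 18–97% (gamma, 1.9) and 7–60% (1.14, both shapes).

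**After the change.** Within-arm Spearman, or a rank regression with an arm term, gives 4.1–5.9% in every scenario.

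**Baseline IgE** (3,000 runs, 120 per arm, CSMS difference 1.9 at mean IgE):

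| Truth | Pooled Spearman | Regression without treatment | Interaction term |
|---|---|---|---|
| No link | 5.2% | 4.6% | 4.5% |
| Prognosis only, 1 point per SD of IgE | 88% | 91% | 4.8% |
| Effect modification, slopes +0.95 (placebo) and −0.95 (active) | 4.4% | 5.0% | 89% |

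The first row shows no artefact. The second and third show that the planned methods detect prognosis and can miss effect modification. The third is an illustration with slopes chosen to cancel when pooled.

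**The case against.** **Pooling is inferred from silence.** Naming the FAS fixes a population, not the handling of arms. That is true, but the same section states the split by treatment for the descriptives and omits it for the correlations, so pooling is the natural reading.

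**Masking is already recognised.** The SAP speaks of detectable IgE, Protocol 9.2.7.2 gives the purpose of the post-dose data, and Protocol 9.2.10 sends the in vitro inhibition assay to a separate report. This stands in part: the claim that inhibition tracks improvement is not formally an output of SAP 5.11. A pooled p-value from that section would still invite it.

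**Stronger readings that the documents do not support.**

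- A reader might infer that masking alone makes the correlation significant. It does not. Without a treatment effect the rate stays at 4–6% whatever the masking, and with one it runs from about 7% to 97% depending on the assumptions.
- A reader might extend the artefact to the baseline correlations or the regression. Those use pre-dose values balanced by randomization.
- A reader might extend it to every IgE measure. The protocol states inhibition for anti-Bet v 1 sIgE only. Masking of birch pollen sIgE is an assumption, and nothing is said of total IgE or unrelated allergens.
- A reader might conclude that response by baseline IgE goes unexamined. SAP 3.5 and 5.6.4 plan forest plots of the CSMS treatment difference by screening birch sIgE (cut at 17.5 kUa/L) and by sensitization status. These are dichotomized and state no interaction test, so they answer the question only in part.

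**Correlation is the endpoint as defined.** Protocol 4.3 does define an endpoint as baseline IgE correlated with the seasonal scores, and SAP 5.11 delivers it. The objective in Protocol 2.3 asks for more.

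**Conclusion.** The point holds for exploratory results only. As naturally read, the V5/V7 correlation for Bet v 1 sIgE is confounded by arm. At the planned CSMS effect it would reach p<0.05 in about 11–79% of trials (normal) or 18–97% (gamma) with no within-arm relation. The position in that range depends on the size of masking, which the documents do not give, and on the shape of CSMS. The whole range also depends on the drug working.

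The question about response and in-season sIgE change is left without a usable analysis. The baseline question is partly covered by the subgroup plots, but the regression as written cannot address it. These analyses lie outside the testing hierarchy in SAP 5.6.3, so the primary test and the ranked secondary tests are unaffected.

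**What to change.** In SAP 5.11:

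1. State that V5/V7 IgE correlations are computed within each arm, or as partial correlations given treatment, and name the IgE measures involved.
2. Assess natural in-season change in Bet v 1 sIgE in the placebo arm only. Describe the active-arm values as reflecting competition with the drug.
3. Add treatment and treatment-by-log-baseline-IgE to the regression, and report the interaction estimate with its 95% confidence interval.
4. Change the second use of *dependent* to *independent*.

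The cost is SAP wording and slightly more output, with no new data. Within-arm estimates are less precise: with 120 subjects the standard error of a correlation is about 1/√117 = 0.092, against 1/√237 = 0.065 for 240 pooled. The partial correlation keeps the full sample.
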